9.7. METHODS FOR ANALYSIS OF SECONDARY OUTCOMES

For binary endpoints, after handling of intercurrent events in Section 9.4, the proportion will be summarized with percentage, 95% confidence interval, and compared between the two treatment arms with Fisher's exact test.

9.8. METHODS FOR ANALYSIS OF SAFETY OUTCOMES

Treatment-emergent adverse events (TEAEs) are defined as those that began or worsened in severity after the first dose of the study drug but within 140 days after the last dose of the study drug. The number and percentage of subjects experiencing TEAEs will be tabulated by symptoms, severity, and relationship to the product as assessed by the investigator. Summaries (including percentages and events per 100 patient-years) of SAEs, deaths, and AEs leading to discontinuation will be provided as well. Pre-treatment AEs will be summarized separately, based on data availability. Note that missing safety data will not be imputed. Analysis details will be specified in the SAP.

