Endpoints:	
Primary Endpoint: change from baseline in number and/or effector function of epidermal CD8+CD103+ Trm cells at Week 52 in psoriasis patients treated with 4X standard induction doses of risankizumab (600 mg at Weeks 0, 4, and 16) or 2X standard induction doses of risankizumab (300 mg at Weeks 0, 4, and 16).
 
Secondary Endpoints:
 
 1) PASI 100 (complete clearance) response at Weeks 28, 40, 52, and 100 in patients receiving 4X standard induction doses of risankizumab or those receiving 2X standard induction doses of risankizumab and 2) safety events over 100 weeks in patients receiving 4X standard induction doses of risankizumab or those receiving 2X standard induction doses of risankizumab. 
Additional endpoints:
 
 1) Change from baseline in PASI and BSA at various timepoints, PASI 75 response, PASI 90 response, PASI 100 response, and sPGA 0/1 response at various study timepoints 2) Change from baseline in DLQI at Weeks 28 and 52 and DLQI 0/1 response at Weeks 28 and 52
Study Population:	20 patients with moderate-to-severe plaque psoriasis, males and females, 18 years of age and older, good general health, Portland metropolitan area
Phase:	2
Description of Sites/Facilities Enrolling Participants:	Single center: Oregon Medical Research Center in Portland, Oregon
Description of Study Intervention:	
This is a single-center, randomized, interventional, Phase 2 study (KNOCKOUT) consisting of a 52-week double-blind period followed by a 48-week unblinded extension comparing tissue and clinical effects of 4X standard induction doses of risankizumab vs. 2X standard induction doses of risankizumab in patients with moderate-severe plaque psoriasis.
 
Twenty patients with moderate-to-severe plaque psoriasis will be randomized in a 1:1 manner to receive either risankizumab 600 mg (4X dosing) or 300 mg (2X dosing), subcutaneous (SC), at Weeks 0, 4, and 16. All patients will receive four SC injections at Weeks 0, 4, and 16 (into right arm, left arm, right thigh, left thigh) by an unblinded pharmacist. For patients randomized into the highest induction dose arm, each shot will contain 150 mg of risankizumab; for patients randomized into the 2X induction dose arm, two shots will contain 150 mg of risankizumab each and 2 shots will contain placebo (sterile saline).

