3. OBJECTIVES AND ENDPOINTS

OBJECTIVES	ENDPOINTS	JUSTIFICATION FOR ENDPOINTS

Primary Objective: to determine whether the reduction in the number and/or effector function of epidermal CD8+CD103+ Trm cells at Week 52 (compared to baseline numbers) in psoriasis patients treated with 4X standard induction doses of risankizumab (600 mg at Weeks 0, 4, and 16) is greater when compared to psoriasis patients treated with 2X standard induction doses of risankizumab (300 mg at Weeks 0, 4, and 16).
	
Primary Endpoint: change from baseline in number and/or effector function of epidermal CD8+CD103+ Trm cells at Week 52 in psoriasis patients treated with 4X standard induction doses of risankizumab (600 mg at Weeks 0, 4, and 16) or 2X standard induction doses of risankizumab (300 mg at Weeks 0, 4, and 16).
	
Trm cells are the primary cells within psoriatic lesions (and healed skin) that are responsible for psoriasis recurrences after skin lesions have cleared. Targeting these cells, as proposed here, may lead to prolonged remission of psoriasis.

Secondary Objectives:
 
 1) to compare the percentage of patients with PASI 100 (complete clearance) at Weeks 28, 40, 52, and 100 in patients receiving 4X standard induction doses of risankizumab vs. those receiving 2X standard induction doses of risankizumab and 2) to compare safety events over 100 weeks in patients receiving 4X standard induction doses of risankizumab vs. those receiving 2X standard induction doses of risankizumab. 	
Secondary Endpoints:
 
 1) PASI 100 (complete clearance) response at Weeks 28, 40, 52, and 100 in patients receiving 4X standard induction doses of risankizumab or those receiving 2X standard induction doses of risankizumab and 2) safety events over 100 weeks in patients receiving 4X standard induction doses of risankizumab or those receiving 2X standard induction doses of risankizumab. 	
These are standard measures of efficacy and safety for psoriasis studies.

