9. STATISTICAL CONSIDERATIONS

9.1. STATISTICAL HYPOTHESES

The study is exploratory in nature and is not statistically powered to detect differences between the treatment arms. All analyses will be descriptive with the goal of developing hypothesis-generating data. The statistical analyses will be performed by AbbVie data and statistical sciences (DSS). Complete and specific details of the statistical analysis will be described and fully documented in the Statistical Analysis Plan (SAP). The statistical analyses will be performed using SAS (SAS Institute Inc., Cary, North Carolina, USA).

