9.4. HANDLING OF POTENTIAL INTERCURRENT EVENTS

There will be two major types of intercurrent events (ICE) in this study: risankizumab discontinuation due to lack of efficacy or intolerance, and risankizumab discontinuation due to other reasons. Each intercurrent event will be addressed by different strategies, specifically:

Table ** Handling of Potential Intercurrent Events

Intercurrent Event	Strategy	Description
risankizumab or study discontinuation due to lack of efficacy or intolerance	Composite variable strategy	Data after risankizumab or study discontinuation due to lack of efficacy or intolerance will be set to non-responder for binary endpoints. For continuous endpoints, set to last observation before discontinuation.
risankizumab discontinuation due to other reasons	Treatment policy strategy	Data after risankizumab discontinuation due to other reasons will be used regardless of whether the intercurrent event occurs.

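### The TEAE tables stop at about Week 36, leaving later non-serious AEs without a named summary although the secondary endpoint covers safety to Week 100

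*Combined protocol and SAP*

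**What the plan says.** The Synopsis gives the second secondary endpoint as "safety events over 100 weeks in patients receiving 4X standard induction doses of risankizumab or those receiving 2X standard induction doses of risankizumab". The matching objective in Section 3 is "to compare safety events over 100 weeks in patients receiving 4X standard induction doses of risankizumab", set against the 2X arm.

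Section 9.8 describes the safety analysis. A TEAE must begin, or become more severe, "after the first dose of the study drug but within 140 days after the last dose of the study drug". Three outputs follow:

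- The TEAE tables: "The number and percentage of subjects experiencing TEAEs will be tabulated by symptoms, severity, and relationship to the product as assessed by the investigator".
- A second group, for which no time limit is stated: "Summaries (including percentages and events per 100 patient-years) of SAEs, deaths, and AEs leading to discontinuation will be provided as well".
- A separate summary of AEs before treatment, if data allow.

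Section 8.1 has AEs checked at every visit after baseline, and the note to the Section 1.2 schema has subjects seen every 6 weeks for safety from Week 52 to Week 100. Sections 9.1 and 9.8 leave analysis details to the SAP.

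**The concern.** The endpoint and its analysis cover different periods. All dosing is finished by Week 16, so a window tied to the last dose ends long before follow-up does. A non-serious AE with onset after the window, in a subject who stays in the study, is not a TEAE. Nor does it belong among the deaths, SAEs and discontinuations, or among the pre-treatment AEs. Section 9.8 therefore names no output in which it would appear.

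If the plan is followed as written, the only general AE breakdown covers about the first third of the 100 weeks. After that, the comparison of the arms rests on deaths, SAEs and AEs causing discontinuation, which may be few in 20 subjects. Longer-term safety is a real question in this trial: Section 2.3.1 puts the highest repeated subcutaneous dose tested so far at 180 mg (with higher repeated doses given intravenously), and both arms receive more than 180 mg subcutaneously at each of three visits.

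**Working it through.** **Inputs**

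- Last planned dose: Week 16, Day 112 (Sections 1.3 and 6.1.2)
- TEAE window: 140 days after last dose (Section 9.8)
- End of follow-up: Week 100, Day 700 (Sections 1.3 and 4.4)
- End of double-blind period: Week 52, Day 364 (Sections 1.3 and 6.3)
- Visit window: ±7 days (Section 1.3)
- Subjects: 20 (Section 9.2)

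**The plan's own figure.** Section 4.4 gives 84 weeks of observation after the last dose. (700 − 112) / 7 = 84, an exact match.

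**Window closing date**

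- On schedule: 112 + 140 = Day 252; 252 / 7 = Week 36.
- Week 16 dose 7 days early or late: Day 105 + 140 = 245 (Week 35); Day 119 + 140 = 259 (Week 37).
- Last dose received at Week 4: (28 + 140) / 7 = Week 24. Week 0 dose only: 140 / 7 = Week 20.

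**Follow-up time outside the window (subject dosed on schedule)**

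- 700 − 252 = 448 days; 448 / 700 = 64%. With the visit window, 441 / 700 = 63% to 455 / 700 = 65%.
- Double-blind part: 364 − 252 = 112 days; 112 / 364 = 31%.
- Extension: 700 − 364 = 336 days, all outside. Check: 112 + 336 = 448.

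**Visits.** There are 19 scheduled visits after baseline. The 10 at Weeks 46 to 100 each cover a 42-day interval wholly after Day 252 (10 × 42 = 420 days). The interval ending at Week 40 (Day 238 to 280) is split: 252 − 238 = 14 days inside and 280 − 252 = 28 outside. Check: 420 + 28 = 448. Counted by visit date instead of interval, 11 of 19 visits fall after the cut-off.

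**Patient-years outside the TEAE tables (retention is an assumption)**

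- All 20 complete: 20 × 448 / 365.25 = 24.5 of 20 × 700 / 365.25 = 38.3, or 64%.
- Four leave at Day 252: 16 × 448 / 365.25 = 19.6 of (16 × 700 + 4 × 252) / 365.25 = 33.4, or 59%.

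**Does Section 9.7 fill the gap?** It reads "For binary endpoints, after handling of intercurrent events in Section 9.4, the proportion will be summarized with percentage, 95% confidence interval", followed by Fisher's exact test between arms. It defines no AE set and no period. It also applies the Section 9.4 rule first, under which "Data after risankizumab or study discontinuation due to lack of efficacy or intolerance will be set to non-responder for binary endpoints". Responder status has no meaning for an AE, so Section 9.7 cannot serve as the AE analysis.

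**The case against.** The strongest objection is that Sections 9.1 and 9.8 defer details to a SAP, where a table of all AEs to Week 100 would naturally be specified. That stands as a limit: such a table may be planned elsewhere. But Section 9.8 itself fixes the 140-day definition and says what is tabulated, and the document reviewed contains no SAP rule that changes either.

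Second, the term for safety events is not defined, and deaths, SAEs and discontinuations are safety events too. If those summaries run to Week 100, the endpoint has some analysis over the full period. That is a possible reading, but a narrow one for a plan that collects all AEs at every visit to Week 100. Section 9.8 states no interval for those summaries; if they also stop at 140 days, the gap is wider.

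Third, a 140-day on-treatment window is not an error, and this review does not treat it as one. Fourth, Section 9.8 names no between-arm test for TEAEs either, so the lack of a test is not specific to late AEs. That is correct; what is missing is the by-arm summary itself.

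Finally, this is a 20-subject descriptive pilot, the data are collected anyway, and the table could be produced later. That limits the harm. It does not remove the need to say which summary answers a stated secondary endpoint, and choosing the AE period after seeing the data is weaker than fixing it beforehand.

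**Conclusion.** The concern holds and should be fixed. For a subject given all three doses on schedule, the TEAE tables close at Week 36 (Weeks 35 to 37 with the visit window), leaving 64% of the endpoint's follow-up time (63% to 65%) outside them. The gap does not come only from the extension, since it takes in the last 16 weeks of the double-blind period. It is confined to non-serious AEs with onset after the window that do not lead to discontinuation.

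This rests on reading Section 9.8 as written, and on taking the absence of a stated limit for deaths, SAEs and discontinuations to mean that they run to the end of follow-up. The percentages describe time at risk; the number of AEs affected cannot be derived from the documents. No data are lost.

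**What to change.** Retain the 140-day TEAE table as the on-treatment summary. Add two sentences to Section 9.8 or the SAP, for example:

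> All AEs with onset from first dose to Week 100 or last contact will be summarized by arm, by symptom, severity and relationship, as the analysis of the secondary safety endpoint. Rates for SAEs, deaths and discontinuation AEs will use events and patient-years over that same interval.

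The second sentence is a clarification, because the plan gives no interval for those rates. Splitting the new table at Week 52, when subjects and staff are unblinded under Section 6.3, is optional.

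The cost is the added text and one extra set of tables. No visits, procedures or data items are added, because AEs are already assessed at every visit after baseline.

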9.9. MISSING DATA HANDLING

For the primary analysis, missing data will be assumed as missing completely at random (MCAR). Data after handling intercurrent events will be used as observed.

For sensitivity analysis (as appropriate), missing data will be assumed as missing at random (MAR). Missing data after handling intercurrent events will be imputed by multiple imputation, as appropriate. Details will be documented in SAP.

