1. PROTOCOL SUMMARY

1.1. SYNOPSIS

Title: “Decreasing resident memory T cells while increasing clinical durability: higher induction doses of risankizumab for moderate-to-severe plaque psoriasis (KNOCKOUT)”

Study Description: This is a pilot study that explores whether higher induction doses of risankizumab (2x and 4x standard induction doses) can more effectively target resident memory (Trm) cells within psoriatic lesions, and whether more profound knock-down of Trm is associated with higher levels of complete clearance (i.e., PASI 100) and for longer periods of time.

Objectives: **Primary Objective:** to determine whether the reduction in the number and/or effector function of epidermal CD8+CD103+ Trm cells at Week 52 (compared to baseline numbers) in psoriasis patients treated with 4X standard induction doses of risankizumab (600 mg at Weeks 0, 4, and 16) is greater when compared to psoriasis patients treated with 2X standard induction doses of risankizumab (300 mg at Weeks 0, 4, and 16).

Secondary Objectives:

- 1) to compare the percentage of patients with PASI 100 (complete clearance) at Weeks 28, 40, 52 and 100 in patients receiving 4X standard induction doses of risankizumab vs. those receiving 2X standard induction doses of risankizumab and
- 2) to compare safety events over 100 weeks in patients receiving 4X standard induction doses of risankizumab vs. those receiving 2X standard induction doses of risankizumab

[figure not shown]

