2. **Single cell sequencing and CyTOF imaging:** A 6 mm punch biopsy will be bisected with one half cryopreserved in CryoStor CS10 media (Millipore, Sigma) in a cryogenic vial, and the other formalin fixed for CyTOF imaging and IHC. The CryoStor CS10 media is an optimized preservation media, that is formulated to address the molecular and biological aspects of cells during the cryopreservation process thereby directly reducing the level of cryopreservation-induced delayed-onset cell death and improving post-thaw cell viability and function. Tissue will be stored at -80C until shipping and processing. At processing samples will be rapidly thawed in a water bath in a continuous agitation and placed onto 25mL of cold 1xHBSS (as described Guillaumet-Adkins A, Genome Biology, 45, 2017). Samples will be incubated in 0.4% dispase (Life Technologies) in Hank's Balanced Saline Solution for 30 minutes. Epidermis and dermis are then separated. Epidermis is digested in 0.25% Trypsin-EDTA (Gibco) with 10U/mL DNase I (Thermo Scientific) for 1 hour at 37 °C, quenched with FBS (Atlanta Biologicals), and strained through a 70 µM mesh. Dermis will be minced, digested in 0.2% Collagenase II (Life Technologies) and 0.2% Collagenase V (Sigma) in plain medium for 1.5 hours at 37°C, and strained through a 70µM mesh. Epidermal and dermal cells will be recombined, and libraries will be constructed by the University of Michigan Advanced Genomics Core on the 10X Chromium system. Libraries will then be sequenced on the Illumina NovaSeq 6000 sequencer to generate 151-bp paired end reads with a goal of 10,000 cells, each with approximately 10,000 reads per cell (100 million reads per sample). Data processing including quality control, read alignment, and gene quantification will be conducted using the 10X Cell Ranger software.

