9.6. METHODS FOR ANALYSIS OF PRIMARY OUTCOMES

For the primary outcomes, after handling of intercurrent events as specified in Section 9.4, the change from baseline in the number and/or effector function of epidermal CD8+CD103+ Trm cells at Week 52 will be summarized with mean, standard deviation, 95% confidence interval, and compared between the two treatment arms with t-test. Additional analysis with non-parametric test (e.g., Wilcoxon signed-rank test) will be performed, as appropriate. Details will be provided in the SAP.

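### If effector function is read on the Trm cells themselves, a patient with none left at Week 52 has no function value, and Section 9.9 has no suitable rule for that case

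*Combined protocol and SAP*

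**What the plan says.** - **Endpoint and test (Section 9.6).** The plan says that "the change from baseline in the number and/or effector function of epidermal CD8+CD103+ Trm cells at Week 52 will be summarized" with a mean, standard deviation and 95% confidence interval, and "compared between the two treatment arms with t-test". A non-parametric test may be added. Effector function is not defined, and no value is given for a sample without Trm cells.
- **Missing data (Section 9.9).** "For the primary analysis, missing data will be assumed as missing completely at random (MCAR", and "Data after handling intercurrent events will be used as observed". The sensitivity analysis assumes MAR: "Missing data after handling intercurrent events will be imputed by multiple imputation, as appropriate".
- **Intercurrent events (Section 9.4).** Two types are listed. Both concern discontinuation, one for lack of efficacy or intolerance and one for other reasons.
- **Assays (Section 8.1).** The single-cell analysis determines gene expression for each cell subpopulation. The imaging panel lists lineage, residency and circulating-memory markers, but no cytokine or other effector marker. Bulk RNA-seq is also described.
- **Aim (Section 1.1).** The study asks "whether more profound knock-down of Trm is associated with higher levels of complete clearance", so loss of these cells is the hoped-for result.
- **Size and status (Sections 9.1 and 9.2).** Twenty patients are randomised 1:1. The number rests on feasibility, and the analyses are descriptive.

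**The concern.** A count has a value when there are no cells: it is zero. A property of the cells, such as how strongly they express IL-17A (the product named in Section 2.2), does not. A patient who was dosed, attended and gave an adequate biopsy can therefore lack a function value because treatment removed the cells.

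That missingness depends on the outcome, so MCAR is not credible for it. MAR imputation does not help either, because it would supply a function for cells that are absent.

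If 4X depletes more than 2X, more 4X patients lose their value. If function also falls with depth of knock-down, those patients are the strongest responders. The function comparison is then made among patients with residual cells, and the observed difference tends to be too small. With 10 per arm, each lost patient is 10% of an arm.

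**Working it through.** **1. Trace one patient through the plan.** Take a patient with all doses given, an adequate Week 52 biopsy and no CD8+CD103+ epidermal cells.

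| Component | Value | Section 9.4 | Section 9.9 primary | Section 9.9 sensitivity |
|---|---|---|---|---|
| Number | 0 (observed) | not triggered | kept | kept |
| Function, per cell | none | not triggered | omitted | imputed, if imputation is used |
| Function, per tissue or per total cells | 0 (observed) | not triggered | kept | kept |

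The gap exists only in the middle row. The documents do not say which function row applies. Because the endpoint sets function apart from number, and Section 8.1 determines expression by subpopulation, the per-cell reading is the most natural one.

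**2. How often samples could be empty.** The plan gives no Week 52 Trm frequency, so the shares below are assumptions. Section 8.1 plans a single-cell library "with a goal of 10,000 cells, each with approximately 10,000 reads per cell". Expected Trm cells = 10,000 × share, and the Poisson chance of none is exp(−mean).

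- Share 0.01%: mean 1, P(none) = 0.368.
- Share 0.03%: mean 3, P(none) = 0.050.
- Share 0.1%: mean 10, P(none) = 0.00005, but P(fewer than 10) = 0.458.

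**3. Fixed example (assumed figures).** Baseline is 40% IL-17A-positive among Trm cells, and surviving cells are 30% positive in both arms. No cells remain in 4 of 10 patients on 4X and 1 of 10 on 2X.

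- Observed values only: 30 − 40 = −10 points in each arm, difference 0, on 6 v 9 patients.
- Absent cells scored as zero: 4X is (4×0 + 6×30)/10 − 40 = −22, and 2X is (1×0 + 9×30)/10 − 40 = −13. The difference is −9, on 10 v 10 patients.

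**4. Simulation A (all inputs assumed).** There are 10 patients per arm. Depth d is N(0,1) on 2X and N(1,1) on 4X. Captured cells are Poisson(exp(a − d)). Function is −0.7d plus noise, with total SD 1, so the true difference is −0.70. Patients below the stated number of cells are dropped.

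| a (median cells, 2X) | Minimum cells | Unscorable 2X, 4X | Mean difference after dropping | Wrong sign after dropping |
|---|---|---|---|---|
| 3.5 (33) | 1 | 0.2%, 1.6% | about −0.68 | 6% |
| 1.6 (5) | 1 | 7%, 24% | −0.58 | 11% |
| 3.5 (33) | 10 | 12%, 41% | −0.42 | 19% |
| 2.3 (10) | 5 | 24%, 58% | about −0.37 | 24.5% |

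With nobody dropped, about 6% of trials already have the wrong sign. With noise SD 1 instead of 0.71, that baseline is about 10% and the last row about 30%, while the mean differences are unchanged. If function is independent of depth, the mean difference stays at −0.70 in every row.

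**5. Simulation B (a separate model, true difference −1.00 SD, only zero-cell patients lost).** Mean counts on 4X and 2X were (1, 3), (2, 5) and (3, 10). Zero-cell shares were 51% v 24%, 33% v 14% and 24% v 5%. The observed-only estimate was −1.00 at correlation 0, −0.88 to −0.91 at 0.5, and −0.80 to −0.85 at 0.8. The loss is therefore 0 to 20%.

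**6. Precision.** Losing patients costs precision even without bias. For a two-sided 5% t-test (the level is assumed) at 80% power, the detectable difference is 1.33 SD at 10 per arm, 1.64 at 7 and 2.03 at 5.

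**The case against.** **The patient stays in the primary comparison.** A reader might infer that the deepest knock-downs leave it altogether. They do not: a zero count is an observed, maximal reduction and stays in the test on number. This objection stands and confines the point to function.

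**Per-cell scoring is not stated.** Effector function is undefined. A count of IL-17A-producing cells, or a bulk tissue readout, always has a value. This stands, and makes the point conditional. It does not remove it, because nothing in the text selects one of those measures.

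**Omission is inferred.** Section 9.9 does not say that finding no cells counts as missing, imputation is only as appropriate, and detail is left to a SAP. This stands in part. However, the default is already fixed as MCAR with observed data, and nothing marks this case for a different rule.

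**The numbers are assumptions.** This stands. No Trm share or minimum cell count appears in the documents. The single-cell library recombines epidermis and dermis, so it is not clearly the source of an epidermal endpoint. A reader might also infer from the wrong-sign rates that the bias can turn against 4X. The modelled mean never reverses. Wrong-sign trials reflect sampling noise at 10 per arm on top of attenuation, and some occur with nobody dropped.

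**The study is an unpowered pilot.** True, so no confirmatory test is at risk. A directional distortion can still mislead hypothesis-generating data.

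**Conclusion.** The point holds in conditional form. If function is measured on the Trm cells, an adequate Week 52 sample without them has no function value. Section 9.4 does not address it, and neither rule in Section 9.9 suits missingness caused by the effect under study. Only the function part of the primary comparison is exposed.

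The direction is attenuation towards no difference. It requires both that 4X depletes more and that residual function tracks depth. The size cannot be fixed from the documents. In Simulation A the loss is about 0.02 SD (0.70 to 0.68) to 0.12 SD (0.70 to 0.58) when only zero-cell patients are lost. Simulation B, where up to half of the 4X arm has no cells, gives up to 0.20 SD out of 1.00. A minimum cell count makes it worse (to 0.42 or 0.37 SD out of 0.70). If function is unrelated to depth there is no bias, only lost precision.

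Both simulations take as their benchmark a notional function value for patients without cells, so they indicate scale and are not estimates for this trial. The change should be made, because the gap is specific and cheap to close.

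**What to change.** - **Section 9.9.** For the Trm endpoint, limit missing to no biopsy or failed tissue or assay quality control. State that no Trm cells found in an adequate sample is an observed result, neither dropped nor imputed. Define an adequate sample without reference to the number of Trm cells in it.
- **Section 9.6.** Compare function between arms on a measure that exists for every adequate sample. One example is function-positive CD8+CD103+ cells relative to total cells or tissue, scored zero when none are found. The denominator should come from the assay that measures function: the listed imaging panel has no effector marker, and the single-cell library mixes epidermis with dermis.
- **Reporting.** Show per-cell function beside it, as a descriptive summary among patients with cells. Give the number of zero-cell and non-evaluable patients per arm.

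The cost is a few sentences in Sections 9.6 and 9.9 or the SAP, and no new samples. The downside is that the scored measure mixes cell number with per-cell activity and so overlaps with the number component. That is why the per-cell summary must accompany it.
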